2.6.2 Clinical Studies of Placebo VR

Similar placebo VRs (Ring-004 with no active ingredient) were studied in IPM 024, IPM 013, IPM 015 and MTN-013/IPM 026.

2.7 Behavioral Studies

2.7.1 Acceptability of Dapivirine Vaginal Ring

IPM 011 assessed the acceptability of the vaginal rings of the candidate microbicide dapivirine VR and the placebo VR. The study participants found the ring to be very comfortable (95%), very easy to insert (94%) and remove (92%), and rarely detectable during daily activities. All questionnaire respondents, when asked if they would be willing to use the vaginal ring if shown to be effective for HIV prevention, replied that they would use the VR.¹⁸

In IPM 015, at Week 12, 97% of women found the dapivirine VR to be comfortable and were willing to use the ring if it was found to be effective. Women preferred to wear the ring every day (97%) and reported that the ring did not interfere with their daily activities (89%).¹⁶ In terms of the male partner acceptability, 63% of women reported that their partner did not feel the ring during sex. Of those participants who reported that their partner felt the ring, only 1% reported that this might be or definitely was a problem.¹⁶

2.7.2 Adherence of Dapivirine Vaginal Ring

In IPM 011, 11% of the women experienced ring removal/expulsions, with the most common reason for ring removal/expulsion being 'menses related'. In the majority of cases (64%), the ring was washed and re-inserted.¹⁸

In IPM 015, perfect adherence was reported by 92% of the female participants. Perfect adherence was defined as never having the ring out for more than an entire day. Of the women who reported that the ring had been removed, the most common reason reported by participants for ring removal was cleaning. The most frequent activity associated with expulsion was urination/defecation. Furthermore, 17-36% (Weeks 2-12) of women reported having sexual intercourse while the ring was out of the vagina.¹⁶

2.8 Study Hypotheses and Rationale for Study Design

2.8.1 Study Hypotheses

MTN-023/IPM 030 hypothesizes that the dapivirine VR will be safe and well-tolerated for once-monthly use among healthy, adolescent females.

2.8.2 Rationale for Study Design

Based on *in vitro*, *in vivo*, and *ex vivo* studies described in the Dapivirine VR IB, dapivirine shows great promise as a topical microbicide to prevent HIV-1 infection.

Vaginal rings have already been developed and approved as delivery methods for medications. For example, NuvaRing®, a contraceptive VR made of the copolymer evatane, in which 2.7 mg of ethinyl estradiol and 11.7 mg of etonogestrel are dispersed, has been found to be both effective and acceptable to women. In an acceptability study

15

involving 1,950 NuvaRing® users, 45.5% of women cited that their reason for liking the VR was "not having to remember anything". Further, vaginal rings provide an acceptable alternative method for the consistent delivery of contraception for adolescent youth.^{19, 20} These contraceptive ring data are encouraging as microbicide ring effectiveness will likely correlate with consistent and correct use. It is likely that products that can be applied less frequently will be more acceptable to users, achieve better user-adherence, and may lead to increased effectiveness. Vaginal rings that need only be replaced every 28 days may have benefits over dosage forms that need to be used more frequently, as well as offer a wider choice of microbicide formulations for women if proven effective.

Estring[®] (estradiol vaginal ring) is a VR that is also made from silicone elastomer and contains estradiol to treat local symptoms of urogenital atrophy, since 1993. Prior to the launch of Estring[®], the biological safety of the silicone elastomer was studied in various *in vitro* and *in vivo* test models. The results show that the silicone elastomer is non-toxic, non-pyrogenic, non-irritating, and non-sensitizing.²¹

Femring[®] (estradiol acetate vaginal ring), a cured silicone elastomer hormone replacement product approved in June 2003 by the United States (U.S.) Food and Drug Administration (FDA), treats menopause-induced vasomotor symptoms (e.g., hot flashes) and symptoms of vulvar and vaginal atrophy (e.g., dryness).

Although these rings differ slightly from the IPM ring, the extensive clinical trial and postmarketing experience gained from these products provides further assurance of the safety of silicone elastomer rings as vaginal drug delivery devices. IPM recently evaluated the acceptability and safety of a similar placebo VR in the IPM 011 study (n=170). This study confirmed that the placebo ring was safe and acceptable to users and their male partners.

Pharmacokinetics

Vaginal fluid and blood for PK will be collected at follow-up visits. Tissue and intensive PK sampling have not been included in this safety study. In the event variations in drug levels between this adolescent population and an adult population are noted, additional studies may be considered.

MTN-023/IPM 030 will fill a void in the dapivirine VR research portfolio, providing the necessary safety data in sexually experienced adolescent females. These data will be added to the efficacy data anticipated from MTN-020 and IPM 027.

3 OBJECTIVES

3.1 Primary Objective

Safety

• To assess the safety of dapivirine (25 mg) administered via a silicone vaginal ring in HIV-uninfected adolescent females, when inserted once every 4 weeks during 24 weeks of study product use

3.2 Secondary Objectives

Acceptability

• To evaluate the acceptability of the study VR (dapivirine or placebo) in HIV uninfected adolescent females, when inserted once every 4 weeks for a 24 week period

Adherence

• To evaluate the adherence to the study VR (dapivirine or placebo) in HIV uninfected adolescent females, when inserted once every 4 weeks for a 24 week period

Pharmacokinetics

• To evaluate systemic and local dapivirine exposure

3.3 Exploratory Objectives

Acceptability

• To investigate association between systemic and local drug concentration, ring residual drug levels and acceptability

Adherence

• To investigate the association between systemic and local drug concentration, ring residual drug levels and self-reported adherence measures

Vaginal Microenvironment

• Describe the genital microenvironment over 24 weeks of study product use

4 STUDY DESIGN

4.1 Identification of Study Design

MTN-023/IPM 030 is a Phase 2a, two-arm, placebo-controlled, double-blinded, multisite, randomized trial of dapivirine VR versus placebo VR (a vaginal ring inserted once every 4 weeks for a total of approximately 24 weeks) in sexually experienced, HIVuninfected adolescent females.

4.2 Summary of Endpoints

Primary Endpoints:

- Grade 2 adverse events as defined by the Division of AIDS Table for Grading the Severity of Adult and Pediatric Adverse Events, Version 1.0, Dec 2004 (Clarification dated August 2009), Addendum 1, (Female Genital Grading Table for Use in Microbicide Studies) judged to be related to study product
- Grade 3 or higher adverse events as defined by the Division of AIDS Table for Grading the Severity of Adult and Pediatric Adverse Events, Version 1.0, Dec 2004 (Clarification dated August 2009)

Secondary Endpoints:

- Participant's self-report on multiple components of acceptability via attitudinal questions
- Frequency of VR removals and expulsions
- Dapivirine concentrations in plasma and vaginal fluid

Exploratory Endpoints:

- Participant's self-report on multiple components of acceptability via attitudinal questions
- Frequency of VR removals and expulsions
- Dapivirine concentrations in plasma and vaginal fluid
- Residual amount of dapivirine measured in returned VRs
- Vaginal pH, microflora and biomarkers

4.3 Description of Study Population

The study population will be healthy, HIV-uninfected, sexually experienced, adolescent females who meet criteria outlined in Sections 5.2 and 5.3.

4.4 Time to Complete Accrual

Accrual is expected to be complete in approximately 12 months at each site.

4.5 Study Groups

Approximately 96 females will be randomized in a 3:1 ratio to one of the following study groups:

- Dapivirine (25 mg) VR
- Placebo VR

4.6 Expected Duration of Participation

The expected trial duration for participants is approximately 25 weeks.

4.7 Sites

Sites selected by ATN and MTN Executive Committee will participate in MTN-023/IPM 030.

5 STUDY POPULATION

5.1 Selection of the Study Population

The inclusion and exclusion criteria in Sections 5.2 and 5.3 will be utilized to ensure the appropriate selection of study participants.

5.1.1 Recruitment

Participants will be recruited from a variety of sources across sites, including, but not limited to, adolescent and primary care health clinics, family planning clinics, and gynecology clinics, as well as community-based locations. It is anticipated that all participating MTN-023/IPM 030 sites will have established relationships with adolescent clinics, pediatric group practices, children's hospitals, etc. Participants also will be referred to the study from other local research projects and other health and social service providers serving the target study population. Recruitment materials will be approved by site Institutional Review Boards/Ethics Committees (IRBs/ECs) prior to use per local requirements.

Note: In case of significant incidental findings, study staff, with written permission from the participant and the participant's parent and/or guardian, may contact the medical care provider to inform him/her of the participant's involvement in MTN-023/IPM 030.

5.1.2 Retention

Once a participant is enrolled/randomized in MTN-023/IPM 030, the study site will make every effort to retain the participants in follow-up to minimize possible bias associated with loss-to-follow-up. An average retention rate of 95% will be targeted at each site.

19

All study sites are responsible for developing and implementing local site standard operating procedures (SOPs) to achieve the targeted retention rate. Components of such procedures may include the following:

- Thorough explanation of the study visit schedule and procedural requirements during the informed assent/parental permission process, and re-emphasis at each study visit. Also, as part of the informed consent process, encouragement of participants to discuss potential study participation with their partners and other influential family members.
- Thorough explanation of the importance of both study groups to the overall success of the study.
- Collection of detailed locator/contact information at the study screening visits, and active review and updating of this information at each subsequent visit.
- Use of adolescent-appropriate approaches to visit reminders, such as technology-based reminders will be sent by study staff,
- Immediate and multifaceted follow-up on missed visits

Study sites may use a participant tracking database to facilitate visit scheduling and timely identification and follow-up on missed visits. The protocol team, as well as the MTN Study Monitoring Committee (SMC), track retention rates closely and work with study sites as needed to take any required action to address below-target retention rates.

5.2 Inclusion Criteria

Adolescent females must meet all of the following criteria to be eligible for inclusion in the study:

- 1) Age 15 through 17 years (inclusive) at Enrollment, verified per site SOPs
- Able and willing to provide written informed assent/consent and able to obtain written parental or guardian permission (as specified in site SOP) to be screened for and to enroll in MTN-023/IPM 030
- 3) Able and willing to provide adequate locator information, as defined in site SOPs
- 4) Able to communicate in spoken and written English
- 5) Able and willing to comply with all study procedural requirements
- 6) Per participant report at Screening and Enrollment, willing to abstain from inserting anything into the vagina for 72 hours prior to each follow-up visit, including abstaining from penile-vaginal intercourse

Note: In the event the vaginal ring has been expelled and requires reinsertion, repositioning the vaginal ring is permitted

- 7) In general good health as determined by the Investigator of Record (IoR)/designee at Screening and Enrollment
- 8) Assessment of onset and progression of puberty, as measured by Tanner stage 4 or 5 at Screening, per participant report and/or clinician assessment
- 9) HIV-uninfected based on testing performed at Screening and Enrollment (per protocol algorithm in Appendix II)
- 10) Per participant report at Screening, history of sexual intercourse (at least one episode in participant's lifetime)
- 11) Per participant report at Screening and Enrollment, agrees to use condoms for sexual intercourse
- 12) Negative pregnancy test at Screening and Enrollment
- 13) Per participant report, using an effective method of contraception for at least 30 days (inclusive) prior to Enrollment, and intending to continue use of an effective method for the duration of study participation; effective methods include:
 - hormonal methods (except contraceptive ring)
 - intrauterine device (IUD)
 - sterilization (of participant, as defined in site SOPs)
- 14) At Screening and Enrollment, participant states a willingness to refrain from inserting the following vaginal products and/or objects into the vagina; spermicides, diaphragms, contraceptive vaginal rings, menstrual cups, cervical caps (or any other vaginal barrier method), douches, lubricants, for the 5 days prior to Enrollment throughout the duration of study participation.

Note: Neither the use of tampons or sex toys, nor participant engagement in coitus is restricted.

15) At Screening and Enrollment, agrees not to participate in other research studies involving drugs, medical devices, vaginal products, or vaccines for the duration of study participation, unless approved by the PSRT

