6.7 Use of Intravaginal Medications/Products and Practices

All participants will be counseled to avoid the use of non-study vaginal products during the period of their study participation. Concomitant use of the following vaginal products or other devices are prohibited for the 5 days prior to Enrollment throughout the duration of study participation: spermicides, diaphragms, contraceptive vaginal rings, menstrual cups, cervical caps (or any other vaginal barrier method), douches, and lubricants. Participants who report use of these products during study product use periods will be counseled regarding the use of alternative methods. These products will be recorded on forms designed for that purpose and study staff should reference Section 9.3 for temporary hold and/or permanent discontinuation guidelines. Oral or parenteral medications are preferred, when at all possible, to avoid the use of vaginal medications. Please note, neither the use of tampons or sex toys, nor participant engagement in coitus is restricted, however, participants will be instructed to abstain from these practices and from inserting any non-study vaginal products for 72 hours prior to each monthly follow-up visit, including abstaining from penile-vaginal intercourse. Participant report of sexual intercourse in the past 72 hours will be assessed at each follow-up visit where samples are to be collected for PK. Visits need not be rescheduled in the event that a participant reports inserting anything into the vagina in the 72 hours preceding the study visit, see the MTN-023/IPM 030 SSP Manual available at www.mtnstopshiv.org.

Condoms will be provided to study staff for distribution to participants.

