7.3 Visit 2: Enrollment Visit (Day 0)

Enrollment Visit procedures are to be conducted at a single visit.

Table	5:	Enrollment	Visit
	•••		

0		Enrollment Visit
Component		Procedures
Administrative and Regulatory		 Confirm eligibility Review/update locator information Randomization Provide reimbursement Schedule next visit and/or contact*
Behavioral/Counseling		 Administer baseline behavioral assessment Provide counseling HIV/STI risk reduction Protocol adherence Product adherence HIV pre and post-test Male condom*
Clinical		 Review/update medical history Review/update menstrual history Review/update concomitant medications Perform full physical examination Perform pelvic examination Including an assessment of cervical ectopy Provide contraceptive counseling Disclosure of available test results Treat for UTIs/RTIs/STIs or refer*
	Urine	 Collect urine for: hCG NAAT for GC/CT, at sites with capacity* Dipstick UA and/or urine culture, per local standard of care*
	Blood	 Collect blood for: Plasma archive HIV-1 serology (confirmatory tests as needed) Serum chemistries* CBC with platelets* Syphilis serology (confirmatory tests as needed)*
Laboratory	Pelvic Samples	 Collect pelvic samples: Vaginal swab for Gram stain Vaginal swab for quantitative vaginal culture Vaginal swab for biomarkers Vaginal pH Cervicovaginal Lavage (CVL) for biomarkers Saline wet mount for BV* KOH wet mount for candidiasis* Vaginal swab for rapid Trichomonas test, at sites with capacity* Vaginal swab for Trichomonas/GC/CT** Herpes lesion testing*
Study Product Supply		 Participants will receive study VR, study VR use instructions and will be instructed to self-insert the study VR Clinician directed digit exam to check vaginal ring placement Note: If the participant is not able to self-insert the study VR, the clinician/designee may assist

Enrollment Visit		
Component Procedures		
Provide male condoms*		
* If indicated/peeded * At sites using Antime only		

* If indicated/needed * At sites using Aptima only

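### The 72-hour abstinence request covers follow-up visits but not Enrollment, so within-arm contrasts of the vaginal microenvironment with Day 0 are partly confounded with recent intercourse or other insertion

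*Protocol*

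**What the plan says.** Criterion 6 in Section 5.2 requires that a participant be "willing to abstain from inserting anything into the vagina for 72 hours prior to each follow-up visit, including abstaining from penile-vaginal intercourse". Screening and Enrollment appear in that criterion only as the occasions on which she states her willingness. Section 6.7 gives the same instruction "for 72 hours prior to each monthly follow-up visit, including abstaining from penile-vaginal intercourse".

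A different restriction applies before Enrollment. Criterion 14 rules out a list of products ending "douches, lubricants, for the 5 days prior to Enrollment throughout the duration of study participation", and its note adds: "Neither the use of tampons or sex toys, nor participant engagement in coitus is restricted".

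On recording, Section 6.7 says: "Participant report of sexual intercourse in the past 72 hours will be assessed at each follow-up visit where samples are to be collected for PK". Those visits are Weeks 2, 4, 12 and 24 (Section 7.7). Section 6.7 also says that a visit need not be rescheduled when a participant reports an insertion within the 72 hours.

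The Enrollment samples in Section 7.3 include a Gram stain swab and "Vaginal swab for quantitative vaginal culture Vaginal swab for biomarkers Vaginal pH Cervicovaginal Lavage (CVL) for biomarkers". The exploratory objective in Section 3.3 is: "Describe the genital microenvironment over 24 weeks of study product use".

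**The concern.** The baseline and all the later samples are collected under different instructions. Before Day 0 a participant is free to have intercourse or use tampons. Before Weeks 4, 12 and 24 she is asked to do neither for three days. The request starts to apply at the same point as ring use, so a before-and-after difference within one arm cannot separate the two.

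At stake is how pH, microflora and biomarker trends are read. If recent intercourse or other insertion moves these measures, a trend from Day 0 could be credited to the ring when part of it comes from the changed instruction, or a real change could be partly masked. The Day 0 sample also cannot be retaken once the ring is in place, so the gap has to be closed before enrollment.

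**Working it through.** **1. Which visits fall under the rule.** The microenvironment samples, by visit (protocol Sections 7.2 to 7.4 and Appendix I):

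| Visit | Gram stain, culture, swab biomarkers | Vaginal pH | CVL biomarkers | 72-hour request | 72-hour intercourse question stated |
|---|---|---|---|---|---|
| Screening | no | if indicated | no | no | no |
| Enrollment | yes | yes | yes | no | no |
| Week 4 | yes | yes | no | yes | yes |
| Week 12 | yes | yes | yes | yes | yes |
| Week 24 | yes | yes | yes | yes | yes |

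Enrollment is the only scheduled pre-ring sample, and it is the one sampling point of the four outside the rule. Weeks 4, 12 and 24 share the same conditions. The 5-day ban before Enrollment already covers douches, lubricants, spermicides and the other listed products. What remains open is intercourse, tampons, sex toys and other unlisted insertions.

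**2. Which contrasts are affected.** Let p0 and p1 be the shares of women with intercourse in the past 72 hours at Enrollment and at a follow-up visit, and d the shift this causes in a measure. With no ring effect:

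- Within one arm, expected change = (p1 − p0) × d.
- Between arms, expected difference in change = (p1 − p0) × d − (p1 − p0) × d = 0, because both blinded, randomized arms follow the same rule.
- Among Weeks 4, 12 and 24, the same request applies at each visit, so the rule itself creates no difference.

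**3. How large it might be.** The protocol states no figure to reproduce. Every value of p0, p1, d and the SD below is an assumption; only the arm sizes, 72 and 24, come from the protocol (Section 10.4.1).

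*pH scale: p0 = 40%, d = 0.6 units, SD of change 0.8 or 0.6, n = 72, two-sided paired t-test at 5%.* The absolute spurious change is (p0 − p1) × 0.6.

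| p1 | Spurious change | Rejection rate, SD 0.8 | Rejection rate, SD 0.6 |
|---|---|---|---|
| 0% | 0.40 × 0.6 = 0.24 | 71% | 92% |
| 10% | 0.30 × 0.6 = 0.18 | 47% | 71% |
| 20% | 0.20 × 0.6 = 0.12 | 24% | 39% |
| 40% (same as Enrollment) | 0 | 5% | 5% |

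*SD scale: residual SD 1, within-person correlation 0.5, normal approximation.* The variance of the change is 2 × (1 − 0.5) + d² × [p0(1 − p0) + p1(1 − p1)].

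| d | p0 | p1 | Bias (SD) | Rejection rate, n = 72 | Rejection rate, n = 24 |
|---|---|---|---|---|---|
| 0.3 | 20% | 0% | −0.06 | 8% | 6% |
| 0.5 | 40% | 10% | −0.15 | 23% | 11% |
| 1.0 | 60% | 10% | −0.50 | 96% | 57% |
| any | equal | equal | 0 | 5% | 5% |

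For the second row at n = 72, the variance is 1 + 0.25 × (0.24 + 0.09) = 1.0825 and the non-centrality is 0.15 / √(1.0825 / 72) = 1.22, which gives 23%.

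The span from 8% to 96% shows that the size cannot be known from the protocol. The result that holds throughout is that the artefact disappears when conditions at the two visits match.

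**The case against.** Several counter-arguments are sound and limit the point.

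- **The objective describes; it does not test change.** Section 3.3 speaks of the period of product use, and Weeks 4, 12 and 24 are on an equal footing. This stands: only contrasts with Day 0 are affected.
- **A reader might infer that Section 10.8.2 commits the trial to paired tests of pH or biomarkers.** It does not. The sentence on within-group change is generic and names no microenvironment endpoint, although it could be applied to one.
- **A reader might infer that the gap could hide harm from the ring.** A ring effect is properly judged against the concurrent randomized placebo arm, and that contrast is not biased. With only 24 women on placebo, some may lean on within-arm trends, but that is a matter of interpretation.
- **A reader might infer that the mismatch can never be adjusted for.** Section 7.3 includes a baseline behavioral assessment of unstated content, which may capture recent intercourse. Section 7.8.1 places sexual activity and intravaginal practices at the monthly visits without naming Enrollment. The supportable statement is that recording at Enrollment is not stated.
- **The mismatch may be small.** Follow-up abstinence is requested but not enforced by rescheduling, participants agree to use condoms (criterion 11), and eligibility needs only one lifetime episode of intercourse (criterion 10). All three are correct, and they are why the rejection rates that assume full follow-up abstinence cannot be taken at face value.

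None of these gives Enrollment the same collection conditions as the later visits.

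**Conclusion.** The point holds in a limited form. Within-arm contrasts of Weeks 4, 12 and 24 with Day 0 are partly confounded with recent intercourse or other insertion, because the request and the stated 72-hour question begin only after Enrollment. Only an exploratory objective is touched. The primary safety endpoints do not depend on it.

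The asymmetry itself is read directly from the text and needs no assumption. Its numerical effect rests wholly on assumed exposure shares, shifts and SDs. Direction is also unknown: a reader might expect a spurious improvement, but the protocol supplies nothing on how intercourse moves these measures or how often it precedes either visit. This is an optional improvement, not a defect that threatens the trial's conclusions.

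**What to change.** 1. In Section 5.2 (criterion 6) and Section 6.7, extend the 72-hour request to the Enrollment Visit as well as each follow-up visit. Reconcile the note to criterion 14, which at present leaves coitus, tampons and sex toys unrestricted without mentioning the 72-hour exception.
2. Keep the existing rule that a visit need not be rescheduled.
3. Record intercourse and other insertion in the past 72 hours at Enrollment and at Weeks 4, 12 and 24. The present question is stated for intercourse only and for follow-up only. If the baseline behavioral assessment already holds such an item, say so in Section 7.8.1.
4. Repeat any change-from-baseline summaries in women abstinent at both time points, and rest any statement about a ring effect on the between-arm contrast.

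The cost is a few words in two sections, one counselling point at Screening and one question at Enrollment, with no added visit or sample. The downside is a small extra request to participants before Enrollment. If the request is thought too much, adding the Enrollment question alone would still allow the mismatch to be described and adjusted for.
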